The aim of the study is to test the feasibility of the study protocol before a future large-scale RCT.

Methods

CONSORT Methods

This pilot trial is a randomized, controlled, two-armed study with a sample size of 30 patients. A sample size of 30 is chosen as a convenience sample. The study will be conducted in Ryhov county hospital, in southern Sweden. Hospitalized patients across adult somatic wards with difficult intravenous access, are screened for potential trial recruitment. Patients are identified when staff from the ward contact the vascular access nurse. All inclusion and exclusion criteria are presented in Table 1. Patients identified, screened, and deemed eligible will be approached with study information. The trial is planned in accordance with the CONSORT guidelines for pilot trials (19).

Table 1 Inclusion and exclusion criteria

Inclusion Criteria	Exclusion Criteria

• Age 18 and over• DIVA criterium fulfilled;
○ 2 attempts of venous access by 2 cliniciansOR○ No visible nor palpable veinsOR○ History of difficult venous access• 4 - 29 days of catheter dwell time anticipated as assessed by referring clinician.	
• Unable to speak Scandinavian• Cognitive Impairment• Is to receive hyperosmolar solutions (600 milliosmoles/L or above).• Is to receive chemotherapy

Setting

The patient flowchart, depicted in Figure 1, outlines the vascular access procedures at Ryhov County Hospital. This process involves collaboration between a ward nurse and an anesthesia (vascular access) nurse. In case the ward nurse encounters difficulties in establishing venous access, patients are referred to the anesthesia nurse accordingly.

[figure not shown]
The insertion of catheters occurs in a dedicated post-op area. Clinicians in this setting have the option to choose between establishing a Midline catheter guided by ultrasound or opting for a Central Venous Catheter (CVC), also guided by ultrasound (USG).

Recruitment, Randomization and Blinding

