Catheter care

Catheters (Midline and CVC) are controlled daily by the ward nurse. Control includes inspection of dressing, puncture site, the catheter itself and tags. The catheter function is assessed and flushed with minimum 20mL saline solution daily and in conjunction to use. For CVCs dressing is replaced every third day or earlier if necessary. Extension tubing, three-way connectors and injection valves are replaced every third day or earlier if necessary. With Midline, StatLock™ Stabilization device is replaced every 7th day or earlier if necessary.

Outcomes

The main outcomes are related to feasibility. Feasibility is defined as eligibility (>50% of screened patients considered eligible), recruitment (>70% of eligible patients consent to partake in trial), retention and attrition (<10% of patients lost to follow up, including those who withdrew consent), adherence (>80% of enrolled patients receive their randomized intervention), missing data (<10% of enrolled patients data missing) and venipuncture attempts (<20% of enrolled patients receive 2 venipunctures per insertion).

The secondary outcomes are insertion time and dwell time measured in minutes and days respectively. Catheter complications (infection, thrombosis and mechanical failure) are measured by objectively through bacterial culture, radiology and clinical expertise as per

standard clinical routine. Catheter complications during insertion and reason for removal are also registered during follow-up.

Follow-up

Follow-up will be performed in-ward every Monday and every Thursday by a research nurse or research assistant. Follow-up will be performed until the catheter is removed or until 28 days. Patients who are discharged from hospital with their catheter in situ will be followed through telephone interviews and chart reviews of out-patient notes

Ethical considerations

Ethical approval from the Swedish Ethical Review Authority is mandatory prior to trial start. The trial will be carried out in accordance with the study protocol under the principles of the Helsinki Declaration. The trial and study protocol will be prospectively registered on www.clinicaltrials.gov.

Regardless of whether a patient participates in the study, the need for venous access remains. Both midline catheters and CVCs are well-established methods for securing venous access, and the study presents no significant disadvantages or ethical concerns associated with their implementation.

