Participation in the trial is entirely voluntary and is based on informed and signed consent. Participants have the right to withdraw their consent at any time for any reason, without prejudice to their medical care. Comprehensive oral and written information about the trial will be provided to participants before obtaining their consent and before their inclusion in the study. The research material will be stored in a secure safe where the research team have exclusive access.

Statistical analysis

Descriptive statistics are used to outline patients' baseline characteristics. For measurements that follow a normal distribution, group differences will be assessed using Student's t-test. Given the small sample size of 30, Mann-Whitney U test will be used to calculate differences in dwell time and insertion time between groups.

Funding

[name] has 25% part-time research funded by RJL and LiU.

Time plan (revised December 2024):

2024 Q1: Protocol construction

[figure not shown]
2024 Q2: Protocol submitted to Ethics Review Board

2025 Q1: Study start (January 13)

2025 Q2: Data analysis and manuscript

Results

Figure X: Patient flowchart according to CONSORT.

References

5. Witting MD. IV Access Difficulty: Incidence and Delays in an Urban Emergency Department. *The Journal of Emergency Medicine*. 2012;42(4):483-7.

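### Dwell time is a censored time to removal, but the protocol fixes a Mann-Whitney test that cannot use a dwell cut short by loss or withdrawal (minor)

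*Protocol*

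**What the plan says.** - Protocol, Outcomes: "The secondary outcomes are insertion time and dwell time measured in minutes and days respectively".
- Protocol, Follow-up: "Follow-up will be performed until the catheter is removed or until 28 days". Discharge does not end observation: "Patients who are discharged from hospital with their catheter in situ will be followed through telephone interviews and chart reviews of out-patient notes".
- Protocol, Table 1 admits patients with "4 - 29 days of catheter dwell time anticipated as assessed by referring clinician", so the upper end of anticipated dwell lies one day past the end of follow-up.
- Protocol, Ethical considerations: "Participants have the right to withdraw their consent at any time for any reason". The retention criterion under Outcomes is "<10% of patients lost to follow up, including those who withdrew consent".
- Protocol, Statistical analysis: a "Mann-Whitney U test will be used to calculate differences in dwell time and insertion time between groups". The reason given is the small sample of 30.

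The protocol does not say what dwell value a patient receives if the catheter is still in place at day 28, or if the patient is lost or withdraws before removal.

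**The concern.** Dwell time is the time from insertion to removal, and the follow-up rules make it right-censored. A catheter last seen in place on day 10 is known only to have lasted at least 10 days. A plain Mann-Whitney test needs one value per patient and cannot hold that information. The stated reason for choosing it, small numbers, bears on normality and not on unseen removals.

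Two workarounds remain. Dropping the patient loses information, and it loses long dwells selectively if longer-lasting catheters are more exposed to loss. Entering the last day seen records a removal that did not happen and shortens that arm's dwell. At stake is a modest loss of power and some distortion of the dwell comparison, more so if loss differs between arms.

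**Working it through.** The protocol gives no dwell distribution, effect size, alpha or power, so there is no figure of its own to reproduce. Everything below on dwell is an assumption. From the protocol come 30 patients allocated 1:1 (15 per arm), the day-28 end and the loss criterion. Below 10% of 30 means fewer than 3 patients, so at most 2, and 2/30 = 6.7%.

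**1. Catheters in place at day 28.** Take exponential dwell with medians of 7 and 14 days. The share still in place is S(28) = exp(−28 ln2 / median):
- median 7: 2^(−4) = 6.25%, or 0.9 of 15 patients
- median 14: 2^(−2) = 25%, or 3.75 of 15 patients

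Kept at 28, these are ties at the top, and both medians are still estimated correctly. If they were deleted, the median of the remainder would be −ln(1 − 0.5(1 − S(28))) / rate, with rate = ln2 / median:
- median 7: −ln(0.53125) / 0.0990 = 6.4 days
- median 14: −ln(0.625) / 0.0495 = 9.5 days

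A true 7-day difference would then appear as 3.1 days.

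**2. Power, exponential dwell.** Simulation with 15 per arm, two-sided 5%, dwell in whole days, and 6.7% loss spread uniformly over 28 days:

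| Analysis | 7 v 14 days | 7 v 20 days |
|---|---|---|
| Mann-Whitney, complete dwell | 33.6% | 62.4% |
| Mann-Whitney, capped at 28, no loss | 33.0% | – |
| Mann-Whitney, early losses at last day seen | 31.6% | 56.7% |
| Mann-Whitney, early losses dropped, day-28 kept | 31.6% | – |
| Log-rank, complete dwell | 45.6% | 76.4% |
| Log-rank, censored | 41.4% | 69.6% |

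The cost to Mann-Whitney is 33.6 − 31.6 = 2.0 points and 62.4 − 56.7 = 5.7 points. About 0.8 to 1.0 of 30 patients are cut off before day 28 with the catheter in place. With equal medians, rejection stays near 5%.

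**3. Power, Weibull dwell** (shape 1.3, twofold ratio of medians, reference median 7 or 10 days, loss at a random point of each patient's own dwell):
- The day-28 cap alone, with up to about 10% in place, costs at most 0.4 points. Only in an extreme case with 34% in place does it cost more (51.3% to 44.7%).
- At 10% loss with the last day entered, power falls by about 5 to 6 points (for example 52.4% to 46.4%), and the probability of longer dwell moves from 0.712 to 0.700.
- At 10% loss with lost patients dropped, power falls by about 4 points and that probability is unchanged.

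**4. Unequal loss, 20% in one arm and none in the other.**
- Exponential, 7 v 14, loss in the longer-dwell arm, last day entered: 21.7%. That is 31.6 − 21.7 = 9.9 points below the equal-loss case and 33.6 − 21.7 = 11.9 below complete data. Censored log-rank gives 38.1%.
- Weibull, twofold ratio, last day entered: 50.0% to 33.3%. With lost patients dropped: 46.4%.
- Weibull, no true difference, last day entered: the probability moves from 0.50 to 0.454 and rejection is 7.5%. The exponential runs gave 4.8%, so a false difference is possible but depends on how loss arises.

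**The case against.** The strongest reply is that the test works and little is lost. Much of that stands.

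- **The day-28 end.** A reader might infer that Mann-Whitney needs a completed day count for everyone. It does not: a common end of follow-up only creates top ties.
- **The large losses.** A reader might infer that the arm difference would shrink from 7 to 3.1 days, with power near 12%. Those figures require deleting every catheter in place at day 28. The protocol does not say to do so, and 28 observed days are available for each.
- **The log-rank advantage.** A reader might credit the whole gap, such as 31.6% against 41.4%, to handling of censoring. The gap is 33.6% against 45.6% with complete data, because the assumed models have proportional hazards, which favour log-rank. Log-rank itself loses about 4 points to censoring here.
- **Death.** The protocol does not mention it, so it is no part of this point.
- **Few patients.** The loss figure is a feasibility criterion, not a forecast, and follow-up continues after discharge.
- **The analysis plan.** Handling rules for lost patients may stand in a statistical analysis plan that is not shown.

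The last argument does not dispose of the point. The protocol itself fixes the test, and no handling rule lets a plain Mann-Whitney use a dwell known only to exceed the last day seen. What needs changing is therefore the named method.

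**Conclusion.** The point holds as a minor one. The fixed test does not suit a time to removal that loss or withdrawal can cut short. Day-28 catheters are handled validly at almost no cost if kept as top ties; dropping them would bias the dwell comparison towards no difference. Early losses cost about 2 to 6 power points at 7–10% loss. With 20% loss in the longer-dwell arm only, the cost is about 10 points under exponential dwell; under Weibull dwell it is about 17 with the last day entered and about 4 with lost patients dropped.

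All of these sizes rest on assumed dwell distributions and loss patterns. Dwell time is an unpowered secondary outcome, the sample is one of convenience, and the main outcomes are feasibility criteria, so no decision stated in the protocol depends on this test. The better reason for the change is sound estimation of dwell per arm, not the gain in power.

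**What to change.** In Statistical analysis, for dwell time, replace Mann-Whitney with Kaplan-Meier curves by randomised arm and a log-rank test. Censor at day 28, and at withdrawal or loss with the catheter in place, on the last day it was known to be in place. Report per arm the median and the mean dwell restricted to 28 days, with the between-arm difference and 95% CI. Keep Mann-Whitney for insertion time.

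The cost is a sentence or two. Insertion and removal dates are needed for dwell time anyway, and the twice-weekly follow-up supplies the last day seen; no patients or visits are added.

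There are two small downsides:
- Censoring assumes that loss is unrelated to remaining dwell. In the Weibull runs, where loss depended on each patient's own dwell, log-rank with 20% loss in one arm only rejected 7.3% of the time with no true difference.
- At 15 per arm the log-rank test runs slightly above nominal, at about 5–7%. A permutation version may be used.
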